9.7. Body Height, Weight and BMI

Body height measured at Screening in Part 1 will be used to calculate the BMI at each time point in Part 1 and Part 2.

For Part 1, changes in body weight and BMI from baseline (last value observed prior to the first dose of study drug) to end of the Double-blind, Randomized Period and to end of Follow-up Period I (last value observed) will be summarized by treatment group using descriptive statistics (n, mean, SD, median, minimum, and maximum).

For Part 2, changes in body weight and BMI from baseline (last value observed during Followup Period I in Part 1) to end of Maintenance Treatment Period and to end of Follow-up Period II (last value observed) will be summarized for all participants using descriptive statistics (n, mean, SD, median, minimum, and maximum).

For Part 1 and Part 2, the change from baseline is defined as the post-baseline value minus the baseline value. There will not be any imputation for missing values. Body height, weight and BMI data will be listed individually for all participants.

9.8. Concomitant Medication

For Part 1 and 2, prior and concomitant medications will be summarized descriptively by treatment group (treatment cohort for Part 2) using counts and percentages.

Prior medications will be presented separately from concomitant medications. Medications that started before first dose of study drug will be considered prior medications whether or not they were stopped before first dose of study drug. Any medications continuing or starting after study drug will be considered to be concomitant. If a medication starts before study drug and continues after study drug it will be considered both prior and concomitant.

Medications will be coded using World Health Organization Drug Dictionary (WHODD) v. Global B3 March 2021.

9.9. Pharmacokinetic Analysis

The PK analysis is not included in this SAP.

10. Derived Variables

• Change from baseline = value at current time point – value at baseline.

- Annualized change in eGFR from baseline to post-treatment follow up = (Post-treatment follow-up eGFR Baseline) / Duration (in years), where Duration (in years) = (median of post-treatment follow-up assessment dates median of baseline eGFR assessment dates + 1) /365.25
- htTKV (mL/m) = TKV(mL)/participant's height (m).
- htLV = LV(mL)/participant's height (m).
- 2009 CKD-EPI equation:

eGFR (mL/min/1.73 m²) = $141 \times min\left(\frac{scr}{k}, 1\right)^{\alpha} \times max\left(\frac{scr}{k}, 1\right)^{-1.209} \times 0.993^{age} \times 1.018$ [if female]× 1.159 [if black]

where Scr is serum creatinine (mg/dL), κ is 0.7 for females and 0.9 for males, α is -0.329 for females and -0.411 for males, min indicates the minimum of Scr/ κ or 1, and max indicates the maximum of Scr or 1, age = years.

• 2021 CKD-EPIcr_R equation:

eGFR (mL/min/1.73 m²) = $142 \times min\left(\frac{scr}{k}, 1\right)^{\alpha} \times max\left(\frac{scr}{k}, 1\right)^{-1.200} \times 0.9938^{age} \times 1.012$ [if female]

where Scr is serum creatinine (mg/dL), κ is 0.7 for females and 0.9 for males, α is -0.241 for females and -0.302 for males, min indicates the minimum of Scr/ κ or 1, and max indicates the maximum of Scr/ κ or 1, age = years. (Delgado et al, 2021)

• 2021 CKD-EPIcr-cys_R equation:

eGFR (mL/min/1.73 m²) =
$$135 \times min\left(\frac{scr}{k}, 1\right)^{\alpha} \times max\left(\frac{scr}{k}, 1\right)^{-0.544} \times min\left(\frac{scys}{0.8}, 1\right)^{-0.323} \times max\left(\frac{scys}{0.8}, 1\right)^{-0.778} \times 0.9961^{age} \times 0.963$$
 [if female]

where Scr is serum creatinine (mg/dL), Scys is serum cystatin C (mg/L), k = 0.7 (female) or 0.9 (male), $\alpha = -0.219$ (female) or -0.144 (male), min indicates the minimum of Scr/ κ or 1 OR Scys/0.8 or 1, max indicates the maximum of Scr/ κ or 1 OR Scys/0.8 or 1, age = years. (Delgado et al, 2021)

• Age for the calculation of eGFR: Since date of birth is not collected in the study and to avoid the calculation error due to the whole number of age, relative age used for the calculation of eGFR is defined as follows:

Age (years) = Age at Screening + (date of blood sample collection for serum creatinine – date of Inform Consent +1)/365.25, rounded to three decimals.

For all efficacy analyses, the eGFR values will be calculated and rounded to 1 decimal based on equations and age defined above for analysis. However, the calculated eGFRs for efficacy analyses will not impact the determination of the randomization stratification factors.

11. Interim Analysis and Data Monitoring

Data analyses are planned to be conducted for Part 1 after the completion of Part 1 and unblinding of study after completion of Part 1. No interim analysis is planned for the efficacy analysis.

11.1. Independent Data Monitoring Committee (IDMC)

In order to ensure the safety of participants, the sponsor will use an IDMC. An IDMC charter was written to describe the IDMC objectives, schedule for data reviews, and general responsibilities in respect to the study. The IDMC will meet on a regular basis as specified in the Charter. In addition to the pre-determined data review meetings, the IDMC may meet on an *ad hoc* basis in the face of an emerging safety issue. The Committee will have access to unblinded data and will make recommendations to the sponsor without revealing participant treatment assignment. No efficacy assessments will be performed by the IDMC, therefore, no adjustment of type I error is required for the final data analysis.

11.2. Hepatic Events Review Committee (HERC)

In order to adequately characterize the liver safety profile of lixivaptan, additional testing and data collection will be required for any participant who develops clinically significant liver chemistry test abnormalities and/or signs or symptoms of liver dysfunction during the study. The HERC will independently and in a treatment-blinded manner expertly judge attribution to study drug as detailed in the HERC Charter and will communicate in writing with the sponsor and the IDMC. The IDMC reviews data at a study-level and, as such, its recommendations will not be made known to the HERC so as not to bias the HERC when adjudicating participant cases. These two committees are independent and will have a one-way line of communication from HERC to IDMC. The results of the HERC review and adjudication will be incorporated into the reporting of the safety results of the trial.

12. Statistical Analysis and Reporting

Data processing, tabulation of descriptive statistics, calculation of inferential statistics, and graphical representations will primarily use SAS (release 9.4 or higher). If the use of other software is warranted, the final statistical methodology report will detail what software, including version, was used for what purposes.

Continuous (quantitative) variable summaries will include the number of participants (n) with non-missing values, mean (geometric mean for log-transformed data), standard deviation (SD), median, minimum, and maximum.

Categorical (qualitative) variable summaries will include the frequency and percentage of participants who are in the particular category or each possible value. In general, the denominator for the percentage calculation will be based upon the total number of participants

with non-missing data in the study population for the treatment groups, unless otherwise specified.

The minimum and maximum will be reported with the same degree of precision (i.e., the same number of decimal places) as the observed data. Measures of location (mean and median) will be reported to 1 degree of precision more than the observed data and measures of spread (SD) will be reported to 2 degrees of precision more than the observed data.

Percentages will be presented to 1 decimal place, unless otherwise specified.

This study has been early terminated by the Sponsor. Due to only 5 participants being randomized into double-blinded, randomized treatment period in Part 1 and all being prematurely terminated in Part 1 of the study, no statistical analyses will be performed and only a limited set of summary tables will be generated along with the study data listings to facilitate the creation of a synoptic clinical study report.

13. Tables, Listings, and Figures

All listings, tables, and figures will have

- A header showing the sponsor company name, protocol, and page number
- A footer showing the file name and path, the source of the data (ADaM dataset or listing number) and date/time created.

The layouts of tables, listings, and figures are presented in SAP Mock Tables, Listings and Figures. These layouts incorporate all the appropriate table titles, table numbers, and footnotes.

14. Mock Tables, Listings, and Figures

The table, listing, and figure shells will be provided in a separate document.

15. Changes from Protocol

Any analyses that deviated from the study protocol are documented below.

Text in Protocol	Change in SAP	Justification
None	Placebo Run-in Safety Set, Lixivaptan Titration Safety Set, ITT, mITT, PPAS, Lixivaptan Treated Safety Set are added in Section 5 Analysis Population	Those analyses population will be needed to summarize the efficacy or safety data
Analysis safety and efficacy sets for Part 2 in Section 5 Analysis Populations	Re-define as two analysis sets: P2SS for safety and P2EAS efficacy, but summary in Part 2 will be presented by treatment cohort	The revised analysis populations are more appropriate for safety and efficacy analyses in Part 2.
LV for analysis	htLV for analysis	To reduce the variance of LV and normalize to participant's height
Annualized change from baseline in htTKV (htLV)	Annualized percent change from baseline in htTKV (htLV)	Anti-log of annualized change from baseline based on the log- transformed htTKV (htLV) implies the annualized ratio of htTKV (htLV) at the evaluated timepoint to baseline htTKV (htLV). This ratio minus one as expressed as percentage will represent annualized percent change from baseline in htTKV (htLV), but not annualized change from baseline in htTKV (htLV).
None	Lixivaptan treated safety summaries have been added in Section 9.6	To add overall safety after randomization during the entire study for all lixivaptan-treated participants during double-bind phase and/or open-label phase.
Blind sample size re- estimation (BSSR)	BSSR is removed	 BSSR is not needed for the study due to the following: Sample size increased due to the increased power from 85% to 90% BSSR may not be feasible according to the currently projected enrollment

16. **Revision History**

The non-editorial changes made to the statistical analysis plan (SAP) will be recorded in the table below. All changes require a new signature page be completed.

Description of the Change/Reason for Change	Document Version Number Before Change	Date of Change
Original	N/A	N/A

17. References

ASA. (2018) Ethical Guidelines for Statistical Practice. Prepared by the Committee on Professional Ethics, April 2018. http://www.amstat.org/about/ethicalguidelines.cfm

ICH (1998). ICH Harmonised Tripartite Guideline. Statistical Principles for Clinical Trials E9; 1998. https://database.ich.org/sites/default/files/E9_Guideline.pdf

RSS. (2014) The Royal Statistical Society: Code of Conduct, 2014. https://rss.org.uk/about/policy-and-guidelines/code-of-conduct/.

Appendix: Method to Derive the Weight for the Weighted ANCOVA Analysis for the Primary Efficacy Endpoint

The following method is proposed to derive the weight for the weighted ANCOVA analysis for the primary efficacy endpoint if the number of eGFR observations is kept at 3 in the pretreatment baseline period. In order to derive the weight used in the weighted analysis, the following model is considered:

$$y_{i,0,k} = \alpha_i + e_{i,0,k}$$
 where $k = 1, 2, K_{i,0}$ (1)

$$y_{i,j,k} = \alpha_i + \delta_{i,j} + e_{i,j,k} \quad \text{where } k = 1, 2, K_{i,j}$$

$$\tag{2}$$

where $K_{i,0}$ is the number of eGFR observations during the pre-treatment baseline period for subject *i*, and $K_{i,j}$ is the number of eGFR observations during the post-treatment follow-up period for subject *i*, with visit *j* as the visit 22 (Week 52) for completers or mapped regular visits for early dropouts. α_i is a random variable for the "real" eGFR baseline of subject *i*, and this variable will be cancelled out for change from baseline. $\delta_{i,j}$ is a random variable for change from pretreatment baseline for subject *i* to visit *j*. These $\delta_{i,j}$ s are normally distributed, with means being $\delta_{P,j}$ for placebo subjects and $\delta_{L,j}$ for lixivaptan subjects, and variance $\sigma_{\delta,j}^2$. These $\delta_{i,j}$ s are supposed to be independent from subject to subject, and each subject has only one post-baseline visit *j* in the primary analysis. In addition, $\alpha_i s$ are assumed iid normally distributed, $e_{i,j,k}$ are assumed iid N(0, σ^2), and all these random variables are mutually independent. Their average over the $K_{i,0}$ observations at baseline and the $K_{i,j}$ observations at post-treatment follow-up will be:

$$\bar{y}_{i,0} = \alpha_i + \bar{e}_{i,0}, \qquad \text{where } \bar{e}_{i,0} \sim N(0, \, \sigma^2/K_{i,0})$$
(3)

$$\bar{y}_{i,j} = {}_{\alpha i} + \delta_{i,j} + \bar{e}_{i,j}, \qquad \text{where } \bar{e}_{i,j} \sim N(0, \ \sigma^2/K_{i,j}) \tag{4}$$

the distribution of their difference is:

$$\bar{y}_{i,j} - \bar{y}_{i,0} = \delta_{i,j} + \bar{e}_{i,j} - \bar{e}_{i,0} \sim N(., \sigma_{\delta,j}^2 + \sigma^2(1/K_{i,0} + 1/K_{i,j})),$$
(5)

where the mean of the normal distribution is $\delta_{P,j}$ for placebo subjects and $\delta_{L,j}$ for lixivaptan subjects.

In order to estimate the variance components given in (5), a further assumption of all $\sigma_{\delta,j}^2$'s are equal, ie, $\sigma_{\delta,j}^2 = \sigma_{\delta}^2$ is made, since there may not be enough subjects withdraw to stabilized the estimate of $\sigma_{\delta,j}^2$ at some visits. In addition, it is assumed all subjects get 3 eGFR observations at baseline. This assumption is reasonable, since usually subjects follow protocol schedules more strictly at the beginning of the trial and could simplify the estimation of the variance components. Then, a formula of change from baseline can be written similar to (5) for the estimation of the variance components:

$$y_{i,j,k} - \bar{y}_{i,0} = \delta_{i,j} + e_{i,j,k} - \bar{e}_{i,0} \sim N(., \sigma_{\delta}^2 + \sigma^2(1 + 1/3)),$$
(6)

A mixed model with fixed effect factors of treatment nested within visit, replication (for the repeated observations at the post-treatment follow-up in eGFR) will be applied to change from baseline (as the average of the 3 pre-treatment eGFR observations) in eGFR observed at each replication. In this mixed model, replications at the post-treatment follow-up are considered as the repeated measurements, with a compound symmetric variance matrix structure. In this

estimated variance-covariance matrix, the diagonal elements are the estimate of $\sigma_{\delta}^2 + \sigma^2(1 + 1/3)$, and the off-diagonal elements are the estimate of $\sigma_{\delta}^2 + \sigma^2(1/3)$. Solving these two equations will get the estimates of σ_{δ}^2 and σ^2 . With these variance component estimates, the variance given in formula (5) is estimated for each subject. Dividing the estimated variance given in (5) by the subject's trial duration will provide an estimated variance for the subject's annualized change in eGFR. The inverse of this estimated variance will be the weight of the subject used in the primary analysis.

SAS code for the estimation of variance component

PROC MIXED;

CLASS USUBJID VISIT TREATMENT REPLICATION; MODEL CHANGE = TREATMENT(VISIT) REPLICATION; REPEATED REPLICATION/TYPE=CS SUB=USUBJID;

```
RUN;
```

In this estimation of variance components, it is assumed the post-treatment follow-up eGFR observations of early withdrew subjects are mapped into scheduled visits. Since the 4-week scheduled visits in this protocol, for a subject early withdrew the study drug, compared to the subject's last scheduled on-treatment visit, if the first post-treatment follow-up eGFR is observed less or equal to 24 days (= 14 + 7 + 3) after the last scheduled on treatment visit, then the subject's post-treatment follow-up eGFR observations will be mapped to the subject's last scheduled on-treatment visit; otherwise, if the first posttreatment follow-up eGFR is observed less or equal to 52 days (= 28 + 14 + 7 + 3) after the last scheduled on treatment visit, then the subject's post-treatment follow-up eGFR observations will be mapped to the visit, then the subject's post-treatment follow-up eGFR observations will be mapped to the visit, then the subject's post-treatment follow-up eGFR observations will be mapped to the visit after the subject's post-treatment follow-up eGFR observations will be mapped to the visit after the subject's post-treatment follow-up eGFR observations will be mapped to the visit after the subject's last scheduled on-treatment visit; etc.

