8.2. Primary Efficacy Analysis (Part 1)

The primary efficacy endpoint is the annualized change in eGFR (2021 CKD-EPIcr_R), with restriction as defined below, for serum creatinine from baseline (mean of 3 eGFR determinations obtained during Screening and Placebo Run-in Periods, i.e., Visits 1a (or 1b, if required), Visit 2, and Visit 3) to final assessment (mean of 3 eGFR determinations obtained during Follow-up Period I after Week 52 for on-treatment completers or, for participants who discontinue study drug treatment prior to Week 52 [Visit 22], 8 to 28 days following study drug treatment discontinuation).

Restriction refers to all annualized changes in eGFR of participants that discontinued study drug treatment that are greater (or less) than the maximum (or minimum) of the annualized eGFR change based on off-treatment serum creatinine assessments of all on-treatment completers regardless of treatment groups. For such participants, the annualized change in eGFR will assume the maximum (or minimum) value of all on-treatment completers to reduce the impact of the outliers created by the annualized eGFR change in participants that early discontinued study drug treatment.

The primary estimand for the primary efficacy endpoint is the between-treatment group difference in the change from baseline in off-treatment eGFR if all the participants in the PEAS had tolerated and adhered to their treatment for 52 weeks. Potential bias due to randomized participants prematurely discontinuing from double-blind treatment will be handled by annualizing the changes from baseline by multiplying each participant's change from baseline by 365.25 days divided by the duration from the median of the collection dates of the baseline eGFR assessments to the median of the collection dates of the 3 eGFR assessments made during the post-treatment, follow-up period immediately (8-28 days) following study drug discontinuation.

An analysis of covariance (ANCOVA) model with fixed effects for treatment group (0=placebo, 1=lixivaptan) and the randomization stratification factors (CKD stage [CKD2 versus CKD3/4] and Mayo Clinic ADPKD Image Classification [1C, 1D, or 1E]) and the baseline eGFR as a covariate.

The following SAS code will be used for the primary efficacy analysis:

```
PROC GLM ALPHA =0.01;
```

```
CLASS TREATMENT CKD_STAGE MAYO_CLASS;
MODEL ANNUALIZED_CHANGE = TREATMENT BASELINE CKD_STAGE MAYO_CLASS/SOLUTION
SS3 CLPARM;
LSMEANS TREATMENT/STDERR

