8.2.1. Sensitivity Analyses of the Primary Efficacy Endpoint

8.2.1.1. Primary Sensitivity Analyses

Sensitivity analyses on the primary efficacy endpoint will be performed using the same ANCOVA model as the primary efficacy analysis with fixed effects for treatment group and the randomization stratification factors (CKD stage [CKD2 versus CKD3/4] and Mayo Clinic ADPKD Image Classification [1C, 1D, or 1E]) and the baseline eGFR as a covariate.

Two sensitivity analyses will be performed on the mITT:

- The annualized change in eGFR (2021 CKD-EPIcr_R) without restriction from baseline to off treatment assessment after Week 52 (mean of 3 eGFR values obtained during off-treatment follow-up visits after Week 52); missing data are handled by multiple imputation:
 - MAR (Section 6.1.4.1.1)
- The annualized change in eGFR (2021 CKD-EPIcr_R) with restriction from baseline to final assessment (mean of 3 eGFR values obtained during Follow-up Period I after Week 52 for on-treatment completers or, for participants who discontinue study drug treatment prior to Visit 22, during the Follow-up Period 8 to 28 days following study drug treatment discontinuation); missing data are handled by multiple imputation:
 - MAR (Section 6.1.4.1.1)
 - MNAR and tipping point analysis (Sections 6.1.4.1.2 & 6.1.4.1.3)

Two sensitivity analyses will be performed on the PEAS:

- The annualized change in off-treatment eGFR (2021 CKD-EPIcr_R) without restriction from baseline to final assessment (mean of 3 eGFR values obtained during Follow-up Period I after Week 52 for on-treatment completers or, for participants who discontinue study drug treatment prior to Visit 22, during the Follow-up Period 8 to 28 days following study drug treatment discontinuation)
- The annualized change in eGFR (2009 CKD-EPI) with restriction from baseline to final assessment (mean of 3 eGFR values obtained during Follow-up Period I after Week 52 for on-treatment completers or, for participants who discontinue study drug treatment prior to Visit 22, during the Follow-up Period 8 to 28 days following study drug treatment discontinuation)

One sensitivity analysis will be performed on the on-treatment completers of the PEAS :

• The annualized change in eGFR (2021 CKD-EPIcr_R) without restriction from baseline to final assessment (mean of 3 eGFR values obtained during Follow-up Period I after Week 52 for on-treatment completers or, for participants who discontinue study drug

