8.2.1.2. Secondary Sensitivity Analyses

Sensitivity on the annualized change in eGFR (2021 CKD-EPIcr_R) with restriction from baseline to final assessment (mean of 3 eGFR values obtained during Follow-up Period I after Week 52 for on-treatment completers or, for participants who discontinue study drug treatment prior to Visit 22, during the Follow-up Period 8 to 28 days following study drug treatment discontinuation) using a weighted ANCOVA will be performed on the PEAS. The weighted analysis is based on the reciprocal of the estimated variance of the "estimated slopes" for participants based on individual off-treatment eGFR values obtained during Follow-up Period I after Week 52 for on-treatment completers or, for participants who discontinue study drug treatment prior to Visit 22, during the Follow-up Period 8 to 28 days following study drug treatment for participants based on individual off-treatment eGFR values obtained during Follow-up Period I after Week 52 for on-treatment completers or, for participants who discontinue study drug treatment prior to Visit 22, during the Follow-up Period 8 to 28 days following study drug treatment prior to Visit 22, during the Follow-up Period 8 to 28 days following study drug treatment discontinuation). The detailed algorithm to derive the weight is provided in an Appendix.

The weighted ANCOVA model will include fixed effects for treatment group and the randomization stratification factors (CKD stage [CKD2 versus CKD3/4] and Mayo Clinic ADPKD Image Classification [1C, 1D, or 1E]) and the baseline eGFR as a covariate.

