8.2.1.3. Exploratory Sensitivity Analysis

The annualized change from baseline in eGFR theoretically contains natural disease progression due to no treatment such as a period for placebo run-in or a period between the last treatment and serum creatinine assessment. To explore the hypothetical treatment effect, a sensitivity analysis will also be performed on the PEAS based on all the changes from baseline in off-treatment eGFRs (2021 CKD-EPIcr_R) that are assessed after 8 days off treatment after randomization in Part 1. The linear mixed effect model with effects of pre-randomization time, off-treatment time, on-treatment time, treatment-by-on-treatment time, randomization stratification factors (CKD stage [CKD2 versus CKD3/4] and Mayo Clinic ADPKD Image Classification [1C, 1D, or 1E]), and eGFR baseline will be used to fit the eGFR data. Intercept, pre-randomization time are both a fixed effect and a random effect. An unstructured variance-covariance matrix is used for modeling.

PROC MIXED EMPIRICAL;

CLASS TREATMENT CKD_STAGE MAYO_CLASS USUBJID; MODEL CHANGE = BASELINE PRIOR-TIME OFF-TIME ON-TIME ON-TIME*TREATMENT CKD_STAGE MAYO_CLASS;

RANDOM INTERCEPT PRIOR-TIME/TYPE=UN SUB= USUBJID; ESTIMATE "Annualized Change from Baseline in eGFR in Lixivaptan Group" BASELINE 1 ON-TIME 1 ON-TIME*TREATMENT 0 1; ESTIMATE " Annualized Change from Baseline in eGFR in Placebo Group " BASELINE 1 ON-TIME 1 ON-TIME*TREATMENT 1 0;

ESTIMATE "Treatment Difference in Annualized Slope of On-Treatment eGFR" ON-TIME*TREATMENT -1 1;

RUN;

where:

- Treatment group (TREATMENT) is coded as 0=Placebo and 1=lixivaptan
- Total time (years) for each off-treatment eGFR = elapsed time from baseline [median date of 3 baseline eGFRs obtained during Screening and Placebo Run-In Periods (Visits1a [1b, if required], Visit 2, and Visit 3) to time of off-treatment eGFR (≥ 8 days off treatment). Total time is divided into three portions: pre-randomization time (PRIOR-TIME), on-treatment time (ON-TIME) and off-treatment time (OFF-TIME).
- Pre-randomization time (years) = elapsed time (years) from baseline to date of randomization
- On-treatment time (years) = time (years) on treatment after randomization, number of treated days with randomized treatment from randomization to date of eGFR assessment/365.25.
- Off-treatment time (years) = Total time (years) for each off-treatment eGFR Prerandomization time (years) - On-treatment time (years).

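### The weights for the weighted ANCOVA divide the raw-change variance by duration once, where the endpoint's definition needs duration squared, so early discontinuers are down-weighted too little under the Appendix's own model

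*SAP*

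**What the plan says.** SAP Section 10 defines the endpoint as "Annualized change in eGFR from baseline to post-treatment follow up = (Post-treatment follow-up eGFR Baseline) / Duration (in years" (the minus sign is lost in the extracted text). Section 4.1.1.1 defines the elapsed duration in the same way, from the median baseline date to the median follow-up date.

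The SAP Appendix builds a model for the change that has not been annualized. Formula (5) gives its variance as σ_δ,j² + σ²(1/K₀ + 1/K_j), with K₀ and K_j the numbers of baseline and follow-up eGFR values. The Appendix then sets σ_δ,j² equal at all visits, "since there may not be enough subjects withdraw to stabilized the estimate of" it at some visits. Next it says: "Dividing the estimated variance given in (5) by the subject's trial duration will provide an estimated variance" for the annualized change. It ends: "The inverse of this estimated variance will be the weight of the subject used in the primary analysis".

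Section 8.2.1.2 is where the weights are used: "Sensitivity on the annualized change in eGFR (2021 CKD-EPIcr_R) with restriction from baseline to final assessment", fitted by weighted ANCOVA on the PEAS, with the reciprocal of the variance of each participant's estimated slope as weight. Restriction is defined in Section 8.2. For a discontinuer whose value lies outside the completers' range, "the annualized change in eGFR will assume the maximum (or minimum) value of all on-treatment completers to reduce the impact of the outliers".

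**The concern.** Inverse-variance weighting works only if the variance belongs to the quantity analysed. Here the quantity is change/T, while the Appendix takes the variance of the change and divides it by T once. The stated purpose is to give less influence to the imprecise annualized values of people who stopped early, and a weight proportional to T does less of this than the Appendix's model calls for.

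There is a second gap. The weights are applied to capped values, and the Appendix never mentions the cap. Formula (5) divided by any power of T therefore describes uncapped values only.

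At stake is one secondary sensitivity analysis and any later trial that copies the Appendix. The primary ANCOVA is unweighted, and the sample size and type I error do not depend on the weights.

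**Working it through.** **Algebra.** Let V be the variance in formula (5). For fixed T, Var(change/T) = V/T², so the weight is T²/V. The Appendix uses V/T and the weight T/V. With V constant over visits, the excess weight of a discontinuer relative to a completer is (T/T_c)/(T/T_c)² = T_c/T.

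**Check by simulation** of the Appendix model, with assumed σ_δ² = 30, σ² = 12 and three values at each end, so V = 30 + 12(1/3 + 1/3) = 38. At T = 0.25 the simulated variance of change/T is 606, against V/T² = 608 and V/T = 152. At T = 1.17 it is 27.6, against 27.8 and 32.5. The two rules agree only at T = 1.

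**Durations.** Take Visit 2 as the median baseline date, 1 week to Visit 3, titration of 5.5 weeks (the plan allows 5 to 6) and Visit 24 on day 18 (range used: 9 to 30). Then T = (1 + 5.5 + weeks on drug + 18/7)/52.18; the one-day offset in Section 10 is ignored. A completer has T_c = 61.07/52.18 = 1.170.

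**Capped values.** The following are assumptions, since the documents give no figures for them. The SD of 6.20 from SAP Section 3.7 is taken as the completers' annualized SD, so V = (6.20 × 1.170)² = 52.7. Changes are normal with equal means. The caps lie at ±3.25 SD = ±20.15, close to the expected extreme of 1080 to 1350 normal completers (3.27 to 3.34 SD). With s = √V/T, c = 20.15 and a = c/s, the capped variance is s²[(2Φ(a) − 1) − 2aφ(a)] + 2c²[1 − Φ(a)]. The correct relative weight is 6.20² divided by that variance.

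| Stop at week | T | Excess, uncapped (T_c/T) | Share capped | SD before / after cap | Correct relative weight, capped | Weight by T | Weight by T² | Excess of T rule, capped (caps at 2.8–4.0 SD) |
|---|---|---|---|---|---|---|---|---|
| 4 | 0.251 | 4.7 | 49% | 28.97 / 16.21 | 0.146 | 0.214 | 0.046 | 1.5 (1.2–2.0) |
| 13 | 0.423 | 2.8 | 24% | 17.16 / 13.52 | 0.210 | 0.361 | 0.131 | 1.7 (1.5–2.1) |
| 26 | 0.672 | 1.7 | 6% | 10.80 / 10.20 | 0.369 | 0.574 | 0.330 | 1.6 (1.4–1.7) |
| 39 | 0.921 | 1.3 | 1% | 7.88 / 7.80 | 0.630 | 0.787 | 0.620 | 1.25 (1.2–1.3) |

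Over the allowed visit timing the uncapped week-4 factor runs from 4.1 to 5.3.

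**Effect on the standard error, capped values.** Participants are assumed to stop evenly over weeks 0 to 52. The 10% rate follows from the protocol synopsis, which assumes 90% complete Part 1; 20% is a stress case.

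| Rule | Model SE / true SE, 10% (20%) | SE / optimum, 10% (20%) |
|---|---|---|
| T, as written | 1.011 (1.020) | 1.003 (1.007) |
| T² | 0.990 (0.981) | 1.001 (1.002) |

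Simulated trials of 1350 (2:1), with caps set at the realised completer extremes, gave model SE / actual SE of 1.009 for T, 0.988 for T² and 0.996 for T² with a sandwich SE at 10%. At 20% the ratios were 1.020, 0.980 and 0.999. On uncapped values T² gave 1.003 at 10%. Monte Carlo error is about 0.5 to 0.7%.

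**The case against.** The algebra is not disputable: no section squares the duration or gives a reason for a single division. The serious objections concern the remedy and the size.

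- **T² alone is not a clear gain on the values the SAP analyses.** On capped values the T rule errs toward too large an SE and T² toward too small a one. At week 4, T² gives 0.046/0.146 = 0.31 of the correct weight. This stands, and it is why the exponent should not be changed without also dealing with the cap.
- **Equal variance over visits is a convenience for estimation.** Section 8.3.1.1 uses a random slope, under which the true-change variance grows with time. With growth in proportion to T, the uncapped week-4 excess falls to 1.2–2.2; with growth in T² it is 0.4–1.6 (single-eGFR noise SD of 2 to 5 assumed). At week 26 the T rule would give 1.04–1.23 or 0.63–0.94 of the correct weight, and T² would give 0.60–0.71 or 0.36–0.54. So T² is right for the Appendix's model and not for every plausible one. The noise term σ²(1/K₀ + 1/K_j), however, needs T² under any of them.
- **The 4.7-fold figure is for uncapped values,** which Section 8.2.1.2 does not specify. This is correct. The factors for the specified analysis are 1.25 to 1.7.
- **A sandwich SE is a new specification here.** The SAP's "PROC MIXED EMPIRICAL" belongs to mixed models, whereas the ANCOVA code in Section 8.2 is PROC GLM. This also stands, though the edit is small.

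**Conclusion.** The Appendix formula is wrong as written. Given the endpoint in Section 10 and the equal-variance assumption, the variance of the annualized change is V/T² and the weight is T²/V. The single division leaves discontinuers with too much weight: about 4.7 times at week 4 and 1.7 times at week 26 on uncapped values, and about 1.5 and 1.6 times on the capped values that Section 8.2.1.2 uses. The capped figures rest on normality, equal means, caps near 3.25 SD and a constant raw-change variance.

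The practical effect is small: a model SE about 1% too large with 10% discontinuing and about 2% with 20%, and an SE less than 1% above the optimum. One secondary sensitivity analysis is affected. SAP Section 12 records that 5 participants were randomized and that no statistical analyses will be done, so no result changes. The correction matters for the record and for reuse of the method. Severity is minor.

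**What to change.** Make the first two changes together.

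1. In the Appendix, divide the variance in (5) by the square of the duration, so that the weight is T²/[σ_δ² + σ²(1/K₀ + 1/K_j)], and define T as the duration in years of Section 10.
2. State that this formula holds for uncapped annualized values. Then choose one of two routes. Either run the weighted ANCOVA on uncapped values, which Section 8.2.1.1 already uses on the PEAS ("The annualized change in off-treatment eGFR (2021 CKD-EPIcr_R) without restriction from baseline to final assessment"), or keep the capped values and report a robust (sandwich) standard error, specified for this model.
3. As a wording point only, the Appendix's closing statement that the weight is for the primary analysis should name the secondary sensitivity analysis of Section 8.2.1.2. Sections 8.2 and 8.2.1.2 already make the intent clear.

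The cost is a few lines in the SAP: one exponent, one definition, a short statement on restriction with the chosen route, and one wording correction. The first route changes the values used in a pre-specified sensitivity analysis; the second adds an SE specification. Neither needs more patients or data, and the primary analysis is unchanged.
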